Intervention. The intervention details and conceptual frameworks underlying this study are previously described. In brief, study clinics received six months of technical assistance in the use of relevant EHR tools and practice coaching in how to use these tools in clinic workflows, both tailored to individual clinics' needs. (The relevant tools in the study clinics' shared Epic EHR supported: identifying patients due for social risk screening; customizing which patients were considered due; documenting and reviewing screening results; and ordering social service referrals.) An EHR trainer and a practice coach guided study clinics through a five-step implementation process: (1) secure leadership buy-in; (2) set goals; (3) develop workflows; (4) orient staff; and (5) implement and iterate. They met with clinic representatives 2-3 times monthly throughout a six-month intervention period, and tracked clinic progress through these steps. All meetings were conducted via video conferencing, a feature intended to enhance the intervention's potential scalability. The intervention was designed to address barriers to social risk screening / referral implementation identified in a prior pilot study (R18DK105463) and as reported in the literature. Prior evidence suggested that each intervention component – practice coaching / facilitation, technical assistance, interdisciplinary support teams, tailored support, staff training, feedback data, goal identification, leadership engagement, peer-to-peer learning, orientation materials, and 'how-to' guides – had the potential to effectively support practice changes in primary care settings.

Study period. The study period was March 2018 through December 2021 and included six 6-month intervention wedges. The first (wedge 1) 6-month intervention began in September 2018, and the last (wedge 6) began January 2021. This allowed for at least six months of data collection before each wedge started, and after the last wedge ended. Thus, all months prior to the 6-month intervention periods were considered 'pre-intervention,' the six months of the intervention were the 'intervention phase,' and all months from the intervention period's end through December 2021 were 'post-intervention.' Of note, wedge 4 began in February 2020 as the COVID-19 pandemic began impacting care delivery in the study clinics.

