Outcome measures. Patient- and encounter-level data were aggregated to the clinic level, limited to persons 18 years or older. Patients seen only for COVID-19 vaccination / testing were excluded (n=3,720; 0.7% of total study sample). Primary analyses centered on social risk screening and related referrals, and

included two outcome measures. The first was the monthly clinic rate of social risk screening, measured as the number of patients with documented social risk screening among those with a face-to-face clinical encounter in the measurement period (excluding those only for COVID testing / vaccination). Domains of social risk screening included child / family care insecurity, education, employment, financial strain, food insecurity, health insurance, health literacy, housing instability, inadequate physical activity, relationship safety, social isolation, stress, transportation needs, and utilities insecurity. The second outcome was the monthly clinic rate of provision of social risk-related referrals, measured as the number of patients with a documented referral among all patients seen in the measurement period (regardless of whether social risk screening was documented). This outcome included referrals internal (e.g., to a social worker) or external to the clinic (e.g., to housing services). As the EHR enabled documenting when patients declined to answer social risk screening questions or declined offered referrals, documented declinations were considered to indicate that screening or referral actions were taken, and included in the numerators described above.

Given the known association between social risks and diabetes outcomes, secondary analyses assessed intervention impacts on diabetes control and receipt of relevant diabetes care. Patients with an encounter during the study period and established diabetes prior to the second month of their clinic's baseline period comprised this subpopulation cohort (excluding pregnant women). Guideline-concordant diabetes-related care was considered monthly for this cohort and included whether patients were up to date on receipt of their (1) annual lipid panel and (2) biannual hemoglobin A1c (HbA1c) screening. Three diabetes control measures were assessed monthly, among patients screened that month: (1) blood pressure (BP; <130/80 mmHg), (2) HbA1c (<7.0%), and (3) low-density lipoprotein (LDL; <100 mg/dL).

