Baseline covariates. The baseline period was defined as the six months before each clinic's wedge began. Analyses accounted for clinic-level baseline measures: number of years since the clinic began using their current EHR; whether the clinic conducted screening at or above the 50th percentile for all study clinics (to capture prior experience with such screening), and patient characteristics aggregated to the clinic level. We also accounted for whether the clinic was concurrently involved in the Centers for Medicare and Medicaid Services (CMS) Innovation Center's Accountable Health Communities (AHC) Model, a large national demonstration project targeting implementation of social risk screening and navigation services. Participants involved in this demonstration received modest financial incentives but only minimal implementation support.

Statistical analysis. Clinic-level outcomes were monthly from March 2018 through December 2021 (totaling 1,384 monthly time points across 31 clinics). Generalized Linear Mixed Models (GLMMs) were used to assess intervention effect by comparing outcomes during time periods in clinics which had versus had not yet participated in the intervention. GLMMs were used to account for a general time trend and flexibly model the intervention effect over time post-intervention. Negative binomial mixed-effects modeling was used to evaluate the primary outcomes; mixed-effects linear regression was used to evaluate secondary outcomes. Each GLMM fit flexible time effects by treating time as a categorical variable and included random effects for clinics, adjusted for baseline covariates, and utilized robust standard errors. Average differences are reported comparing the pre-intervention period to (1) the six-month intervention period and (2) the post-intervention period. Rate ratios (RR) for the primary

outcomes, rate differences for the secondary outcomes, and corresponding 95% confidence intervals (CI) are reported. A more detailed description of the GLMM model is provided by:

The general model is:

$$\log(Y_{it} | b_i) = \beta_0 + \beta_1 t + \beta_2 I_{it}(t - s_i) + \beta_3 Z_i + \theta C + b_i + \log(e_{it})$$

Y_{it} is the number of patients in practice i whom had any SDH data collected during period t .

t is a categorical variable denoting the observation month for t in $(0, 1, \dots, 46)$, where $t = 0$ is the baseline month.

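### The diabetes cohort closes on a date that moves with each clinic's wedge, and no rule starts a patient's contribution at diagnosis; followed literally, this can bias the secondary contrasts.

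*SAP*

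**What the plan says.** The SAP, Outcome measures, builds the diabetes cohort from two conditions. The first is an encounter at any time in the study ("Patients with an encounter during the study period"). The second is a diagnosis date: "established diabetes prior to the second month of their clinic's baseline period comprised this subpopulation cohort". Pregnant women are excluded.

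The denominators follow. For lipid and HbA1c testing, "Guideline-concordant diabetes-related care was considered monthly for this cohort". For control of blood pressure, HbA1c and LDL, "Three diabetes control measures were assessed monthly, among patients screened that month". Neither sentence requires that diabetes be established by the month being counted.

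The calendar comes from two other sections. Under Baseline covariates, "The baseline period was defined as the six months before each clinic's wedge began". Under Study period, "all months prior to the 6-month intervention periods were considered" pre-intervention, "The first (wedge 1) 6-month intervention began in September 2018, and the last (wedge 6) began January 2021", and "wedge 4 began in February 2020". Statistical analysis runs the clinic-level outcomes by month from March 2018 to December 2021. It fits categorical month and random clinic effects, and compares clinics that have taken part with those that have not yet done so. Protocol section 7a likewise has every clinic measured monthly in every period.

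**The concern.** Each clinic's cohort is closed shortly before its own start and then, on the literal wording, followed backwards as well as forwards. A wedge 6 patient diagnosed in mid-2020 is a cohort member and so enters the monthly figures from March 2018, more than two years before diagnosis. Before diagnosis there is less reason to order these tests, and HbA1c values are likely to be lower. In late wedges the early control months would therefore mix people with and without diabetes, and the mixture would thin out as the cut-off approaches. In wedge 1 there is almost no such mixture.

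Those months serve as the comparison for clinics already in the intervention. If they carry this artefact, the secondary contrasts partly reflect how the cohort was built. These contrasts are the SAP's test of whether the intervention improved diabetes care and control.

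**Working it through.** **Plan's own figure.** Thirty-one clinics over 46 months give 31 × 46 = 1,426 clinic-months. The SAP states 1,384, which is 42 fewer; the gap is not explained. If wave 2 clinics (17) had started at their own baseline, at most 14 × 46 + 17 × 29 = 1,137 would exist (all of them placed in wedge 4, which has the earliest wave 2 start). So the clinic series reaches back to about March 2018. The count says nothing about which patients are included.

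**Cut-offs.** Starts are from Study period. The cut-off is the start of baseline month 2, five months before the wedge starts.

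| Wedge | Start | Baseline | Diabetes established before | Pre-intervention months | Of these, before the cut-off |
|---|---|---|---|---|---|
| 1 | Sep 2018 | Mar–Aug 2018 | Apr 2018 | 6 | 1 (17%) |
| 4 | Feb 2020 | Aug 2019–Jan 2020 | Sep 2019 | 23 | 18 (78%) |
| 6 | Jan 2021 | Jul–Dec 2020 | Aug 2020 | 34 | 29 (85%) |

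The cut-offs of wedges 1 and 6 are 28 months apart.

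**Why the model does not remove it.** Let r be the share of the cohort newly established per year, c the cut-off month and t the calendar month (March 2018 = 0). The share not yet diagnosed is r(c − t)/12, floored at zero. With r = 10% (assumed), in March 2018 it is 0.10 × 29/12 = 24% in wedge 6, 0.10 × 18/12 = 15% in wedge 4 and 0.10 × 1/12 = 0.8% in wedge 1. It falls to zero at a different date in each wedge. Month effects are common to all clinics and a clinic effect is constant over time, so neither can absorb a pattern that depends on wedge and month together. Baseline covariates are also fixed per clinic.

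**Illustrative size.** All of the following are assumed: starts of wedges 2, 3 and 5 at months 12, 18 and 29; clinics per wedge 5, 5, 4, 6, 6, 5 (only the wave totals 14 and 17 are stated); no true intervention effect; a linear model with month effects, an exchangeable clinic intercept and two phase indicators, fitted by GLS; and 60% up to date on care after diagnosis, with 50% or 20% before. The bias is proportional to r times the gap. Entries are percentage points, intervention phase / post-intervention.

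| r per year | Gap | ICC 0.1 | ICC 0.9 |
|---|---|---|---|
| 5% | 10 | +0.07 / −0.13 | +0.01 / −0.24 |
| 5% | 40 | +0.27 / −0.53 | +0.04 / −0.97 |
| 10% | 10 | +0.13 / −0.26 | +0.02 / −0.49 |
| 10% | 40 | +0.53 / −1.05 | +0.09 / −1.94 |

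Three variations, all at r = 10%:
- Month effects by recruitment wave, 40-point gap: −0.5 / −1.4 at ICC 0.1.
- HbA1c below 7%, at 45% after and 80% before diagnosis, with testing in the ratio 60:20: the sign turns, to −0.1 / +0.4 at ICC 0.1 and 0.0 / +0.7 at ICC 0.9.
- Effect modelled by month since start and averaged by phase, 40-point gap: −0.37 / −3.16 at ICC 0.1.

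**Effect of each remedy.** Starting a patient at diagnosis removes the pre-diagnosis artefact by construction. It leaves a cohort that stops admitting new diagnoses at different dates by wedge. If care receipt is 10 points lower in the first year after diagnosis (assumed, r = 10%), about +0.55 / +0.83 points remain at ICC 0.1. With one calendar cut-off for all clinics as well, the same calculation gives 0.00.

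**The case against.** The strongest reply is that the literal reading is not the natural one. The SAP speaks of established diabetes, diabetes control and diabetes care, and a programmer may well have counted only months in which a patient had diabetes. What is shown is then a missing denominator sentence, not a biased analysis. This stands in part: nobody can tell from the SAP which rule was programmed. It does not dispose of the point, because the moving cut-off is stated outright and still closes the cohort at different dates by wedge.

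A reader might infer from the 1,384 clinic-months that pre-diagnosis time was in fact counted. The documents do not support that. Starting each patient at diagnosis would leave the count unchanged so long as a clinic had one eligible patient that month, and the figure is not stated to belong to the secondary series.

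A reader might also infer a definite bias of known direction. That is not supported either. Diagnosis rate, outcome gap and ICC are all absent from the documents. Statistical analysis and the Note on protocol deviation may mean effects by month since start, which reverses the intervention-phase sign in the care example. Very low ICCs (0.01 to 0.05) suit patient-level data better than clinic-month aggregates, so they are left out above.

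Finally, a clinic-specific cut-off has a merit: every clinic's cohort is fixed with the same lead time before its intervention. A common cut-off gives that up and changes the late-wedge population. That is why it belongs in a sensitivity analysis and not in place of the main one.

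**Conclusion.** The concern holds as a gap with a conditional consequence. The cut-off dates, the March 2018 start of the series and the absence of an entry rule are all in the text. If the wording was followed, control months in late wedges contain pre-diagnosis time, and the specified model does not remove it. If the programming already counts only months with diabetes, saying so settles that part, and the wedge-dependent closing date remains.

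With 5% to 10% newly established per year, a gap of 10 to 40 points, ICC 0.1 to 0.9 and two phase indicators, the post-intervention bias runs from about 0.1 to 2 points in size. It is larger under a month-since-start model, and its sign depends on the gap and the model. The documents give no standard error or target difference for the secondary outcomes, so they cannot show whether this would change a conclusion. The primary screening and referral outcomes do not use this cohort and are unaffected. The point should be fixed; confidence is medium.

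**What to change.** 1. State the monthly denominator rule for the secondary analyses: a patient counts only from the month in which diabetes is established. Say how that month is determined, since the SAP does not define established diabetes. If this was already the rule, one sentence is enough for this part.
2. Report alongside, as a sensitivity analysis, the same models with one calendar cut-off for all clinics: diabetes established before April 2018, which is the date the SAP already implies for wedge 1.

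The cost is re-deriving the monthly denominators from existing data and re-running the secondary models. Delayed entry drops no cohort member once diagnosed. The common cut-off gives smaller and longer-established cohorts in late wedges. At an assumed 5% or 10% newly established per year, wedge 6 loses r × 28/12, or about 12% or 23%, and wedge 4 loses r × 17/12, or about 7% or 14%. If some of the 42 clinic-months absent from the full grid are early months, the SAP should also say how diabetes before April 2018 is identified in those clinics.

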ASCEND STATISTICAL ANALYSIS PLAN

ASCEND: ApproacheS to CHC ImplEmeNtation of SDH
Data Collection and Action

[NCT03607617](#)

Version: November 18, 2022

ASCEND Statistical Analysis

Data source and trial design. OCHIN, Inc. is a non-profit health center-controlled network. Its members (109 CHC organizations, operating 593 clinic sites in 16 states, as of September 2018) share a single instance of the Epic EHR. This stepped-wedge trial included 31 CHCs recruited from OCHIN's member CHCs; they are located in California, Georgia, Massachusetts, Montana, Ohio, Oregon, Washington, and Wisconsin. Recruitment occurred in two waves (14 in spring 2018 and 17 in fall 2019) to ensure that no recruited clinics waited more than a year for the intervention. Each set of clinics was block-randomized to wedges 1-3 and 4-6, respectively. A stepped wedge trial was chosen as an effective design for when an intervention under study cannot be rolled out simultaneously for everyone yet allows all to eventually receive the intervention. Clinics were eligible to participate if they were interested in implementing or expanding social risk screening / referral activities. They had to commit to identifying staff members to serve as a Clinician Champion and / or Operational Champion for the project and allowing those staff to participate in intervention activities (≥ 2 hours / month interacting with the implementation support team).

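### The SAP names only robust standard errors for 31 clinics, with no small-sample correction or reference distribution; read at face value, its 95% intervals would cover about 92-94%

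*SAP*

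**What the plan says.** The SAP, under Data source and trial design, gives the number of randomised units: "This stepped-wedge trial included 31 CHCs recruited from OCHIN's member CHCs". They came in two waves of 14 and 17, each randomised separately to three wedges.

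Under Statistical analysis the data are clinic-months, "totaling 1,384 monthly time points across 31 clinics". For the model: "Negative binomial mixed-effects modeling was used to evaluate the primary outcomes", with linear mixed models for the secondary outcomes. On time: "Each GLMM fit flexible time effects by treating time as a categorical variable". On variance, the models "included random effects for clinics, adjusted for baseline covariates, and utilized robust standard errors". The general model has one random term per clinic, an intercept. Two contrasts with 95% intervals are reported for each outcome: the six-month intervention phase and the post-intervention phase, each against the pre-intervention period.

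The Protocol adds nothing on variance. Its Analysis Plan (section 7a) says only that GLMMs will be used, and section 8 names SAS without a procedure or option.

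**The concern.** A clinic-clustered sandwich variance draws its information from the number of clinics, not the number of clinic-months. With 31 clinics, about five per wedge, the uncorrected estimator tends to be too small, because fitted residuals are smaller than true errors. Normal critical values then ignore the sampling error of the variance estimate. Both push towards short intervals.

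The SAP leans on this estimator. Each clinic contributes up to 46 monthly observations and the model allows only a clinic intercept. If months within a clinic are autocorrelated, or the effect differs between clinics, valid inference depends on the sandwich. The one sentence quoted above governs both primary outcomes and both contrasts, and also the secondary outcomes. Leaving the variant open means a borderline result could turn on an option that the plan does not fix.

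**Working it through.** Neither document gives a standard error, interval, intraclass correlation or power figure, so there is no stated figure to reproduce.

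**Inputs from the SAP.** 31 clinics (14 in wedges 1-3, 17 in wedges 4-6). March 2018 to December 2021 is 10 + 12 + 12 + 12 = 46 months. On timing: "The first (wedge 1) 6-month intervention began in September 2018, and the last (wedge 6) began January 2021"; wedge 4 began in February 2020. Counting March 2018 as month 0, these starts are months 6, 23 and 34.

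**Assumptions.** Starts of wedges 2, 3 and 5 (months 12, 18 and 29); clinics per wedge (5, 5, 4, 6, 6, 5); and all variance components.

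**Step 1: critical value.** No variance components are needed here.
- Normal: 1.960. t on 30 df: 2.042, ratio 2.042/1.960 = 1.042. t on 29 df: 2.045, ratio 1.0435.
- Adding the simple variance factor 31/30, with √(31/30) = 1.0165: 1.042 × 1.0165 = 1.059, or 5.9% wider. With 25 or 20 df and the same factor: 6.8% or 8.2% wider.
- If the statistic were exactly t on 30 df, a ±1.960 interval would cover 94.1%; on 20 df, 93.6%.

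**Step 2: simulation.** Log rates were treated as normal, with 46 month effects, two phase effects, a clinic random intercept and no true average effect. Clinic SD was 1.0, residual SD 0.6, with six clinic covariates unless noted. Coverage (%) is shown as intervention phase / post-intervention phase. CR3 is the Mancl-DeRouen correction.

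| Month-to-month correlation; SD of effect between clinics | Model-based, z | Uncorrected sandwich, z | 31/30 factor, t(30) | CR3, t(30) |
|---|---|---|---|---|
| 0; 0 | 94.5 / 94.1 | 92.5 / 92.9 | 93.9 / 94.7 | 95.4 / 95.7 |
| 0.7; 0 | 69.4 / 61.7 | 93.5 / 92.2 | 94.7 / 93.7 | 95.6 / 95.1 |
| 0.7; 0.5 | 58.9 / 60.1 | 93.2 / 93.3 | 94.4 / 94.8 | 95.2 / 95.8 |
| 0.7; 0.5, three covariates | 58.2 / 59.3 | 93.4 / 92.8 | 94.4 / 94.6 | 95.4 / 95.7 |
| 0.7; 0.5, repeated with 2,000 runs | – | 93.1 / 92.2 | 94.4 / 93.8 | 95.6 / 95.4 |
| 0.7; 0.5, clinic log-SD 0.5 | – | 93.1 / 92.4 | 94.8 / 93.8 | 95.7 / 94.8 |
| 0.7; 0.5, clinic log-SD 0.8 | – | 93.1 / 95.2 | 94.4 / 96.3 | 95.8 / 97.1 |
| 0.9; 0.5, clinic log-SD 0.5 | – | 94.0 / 93.4 | 94.8 / 94.7 | 95.8 / 95.8 |

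The first four rows used 1,000 runs each and the rest 2,000. Simulation error near 93% is √(0.93 × 0.07/1,000) = 0.8 points, or 0.6 points with 2,000 runs.

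The uncorrected z interval covered 92.2% to 94.0% in 15 of the 16 results; the other was 95.2%. In the first four rows its mean half-width was 0.922 to 0.969 of the half-width implied by the true SD, so the standard error was about 3-8% too small.

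**Step 3: other simulations of the layout.**
- One set used 4,000 runs in each of four variance scenarios, without clinic covariates. Type I error was 6.1-7.6% for the uncorrected sandwich with z, and 3.9-5.0% for Mancl-DeRouen with t(29).
- Another, with clinic covariates, gave coverage of 92.0-94.1% and 94.6-96.3% respectively.

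**Step 4: cost in width.** CR3 with t(30) was 11.4-11.7% wider than uncorrected z in the last four rows. Moving to t(29) multiplies by 2.0452/2.0423 = 1.0014, giving 1.114 × 1.0014 = 1.116 to 1.117 × 1.0014 = 1.119. The simpler 31/30 factor with t(30) costs 5.9%. The range is therefore about 6-12%, with Mancl-DeRouen at the upper end.

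**The case against.** The strongest reply is that the SAP is silent, not wrong. It does not say that the sandwich was uncorrected or that normal critical values were used, and it does not even state the clustering level. If the software applied a t reference and a simple factor, coverage was 93.7-96.3% and little remains to fix. This stands, and it is why the point is conditional.

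A reader might infer that the reported intervals are too narrow. The documents do not support that: they contain no interval or standard error and do not identify the variant. Nor would every interval under-cover even at face value, as the 95.2% result shows.

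A reader might infer that robust standard errors are the mistake. The opposite holds: with month-to-month correlation of 0.7, model-based standard errors covered only 58-69%. A reader might also infer that the 1,384 clinic-months served as the effective sample size. That count only describes the data.

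Clustering by organisation is tempting too, but the SAP does not say whether any of the 31 study clinics share one, so there is no basis for recommending it.

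The simulations are Gaussian stand-ins for a negative binomial model with a patient-count offset. They support the direction and rough size, not an exact shortfall.

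The reply does not dispose of the point. The method as worded, read plainly, falls modestly short, and an unstated software setting is something that a reader cannot verify.

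**Conclusion.** The point holds as a modest, conditional weakness. An uncorrected clinic-clustered sandwich with normal critical values would give the two primary rate-ratio contrasts roughly 92-94% coverage instead of 95%, a type I error of about 6-8% instead of 5%. All three sets of simulations agree on direction and approximate size.

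The figures rest on the normal approximation to the log rate, the assumed variance components, the assumed clinics per wedge and the assumed starts of wedges 2, 3 and 5. Only the change in critical value, 4.35% for t(29), is free of them. The same SAP wording covers the secondary outcomes, but they were not simulated separately, so no figure is claimed for them. Whether the analysis as run has this shortfall cannot be told from the documents.

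**What to change.** Keep the robust standard errors. In the SAP's Statistical analysis section, replace the phrase with: *clinic-clustered robust standard errors with the Mancl-DeRouen small-sample correction and t critical values on 29 degrees of freedom (31 clinics minus 2)*. If a correction and t reference were already used, stating which ones closes the point. If not, re-run the intervals.

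The cost is one sentence and possibly a re-run. Intervals would be about 6-12% wider than uncorrected z intervals, with Mancl-DeRouen near 12%, and slightly conservative in some scenarios: type I error fell to 3.9% in one set, and coverage reached 97.1% with t(30) in another.
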